7.3.6 Back Up Recording

All qualitative interviews may also be recorded using a back-up digital audio recorder. Audio files will be erased after being transcribed and transcripts will be de-identified. All audio files will be kept confidential and stored in a locked/limited access folder on secured servers, which is only accessible to designated study staff. All members of the research team will be trained in confidentiality and have signed confidentiality agreements. A professional transcription service, experienced in the handling of confidential data, will be used to fully transcribe verbatim all audio files. Prior to receipt of the first audio file, the transcription service will be instructed to exclude from the typed transcript identifying information (e.g., a name) that may have been verbalized during the course of the interviews.

7.4 Data Submission

7.4.1 CRFs

Although the iTech projects will involve substantial online follow-up, CRFs will be used to collect key study visit data (e.g., enrollment and randomization assignment), study milestones such as completion or discontinuation, study laboratory results, and adverse events (AE). AC staff will work with study investigators and the MC to develop and design the CRFs. During study conduct, the SRVs will maintain the CRFs in secured locations, and transmit CRF data to the AC either electronically using DFExplore or by submitting scanned paper forms using DFSend. DFExplore and its DFdiscover platform is a leading multi-site database environment for HIV RCT that can receive and transcribe CRF data via scanned PDFs, or allow for direct electronic data entry. It provides for monitoring form completion and data quality, and a system for data querying and resolution with SRVs, while maintaining an audit trail. The AC uses DFExplore for MSM studies and RCTs and data is maintained by the parent company DF/net on a cloud-based server with Microsoft Azure.

7.4.2 Audio-recorded Data

Audio-recorded data from the usability sessions, field testing, and RCT exit interviews will initially be stored as a digital file on a secure encrypted Emory server. Exit interviews will be transcribed verbatim from the digital audio-recording and de-identified by assigning unique numerical codes. After transcripts are verified by the research team and one year after the study is over, audio files will be destroyed.

All CASI data will only be identified with a unique SID and participant code and stored on a secure encrypted server by the AC team. Only SRV research staff, the AC team, and the research team at the University of North Carolina/Duke will have access to the data.

7.4.3 CASI Data Transmission

Survey data will be stored in secure databases on an AC server within the AC data center.

7.4.4 Retention Data

The study will use a HIPAA-compliant web-based platform entitled Study Management and Retention Toolkit (SMART), which is a SaaS (Software as a Service) based mobile application aiding studies with various aspects of participant recruitment, study implementation, and retention. The application has the ability to securely manage participant information across multiple studies and customers simultaneously, stratifying participant information by study and site. SMART includes an admin web portal and a participant facing mobile app (optional), which allows for secure messaging, study calendar management, self-scheduling by participants, secure photo uploads, and longitudinal tracking of participants from screening to study completion. The ability to designate specific roles to all SMART users allows for greater control around permissions and accessibility to participant information. Users can even be limited to a reporting only role, which allows for study oversight through real time aggregate reporting, but no access to PHI. SMART is a licensed service of the Center for AIDS Research (CFAR) at Emory University, Prevention Science Core. Utilization of the mobile app is optional and the admin web portal will fully function without it.

The admin web portal is a web-based application developed using Microsoft .NET technologies. It uses SQL server as backend database. The application requires two servers to host: (1) Web server [Windows server with IIS] and (2) SQL server [Standard or Enterprise version]. Both these servers are to be placed behind a firewall. Web server will have a public IP to access the server using VPN. SSL certificate is to be installed on the web server. The admin website will be rendered over SSL (https).

The application uses form authentication (no integrated authentication such as AD). All passwords are stored encrypted within the database. System will also be using database level encryption, which will prevent any copying of information from one database to another. Web application also uses an automatic logout feature after a certain period of inactivity. By default, the inactivity duration is set to three minutes.

Study staff can only first gain access to the admin web portal if granted by a study or site administrator. Their assigned user role will determine their permissions to perform different actions and even view PHI. Email notifications are sent from the system (without the need to login) when: (1) a staff member requests to reset their password, (2) role assignments to a study are made, (3) an event/visit staff are scheduled to work is nearing, (4) a new task is assigned to a staff member, or (5) they are designated as a staff member to receive alerts of positive test results. All participant communications are performed using secure messaging through the message center (inbox) implementation within the mobile app. If the mobile app is not utilized by a study, communications are sent as standard email or text messages to participants.

7.5 Data Quality Assurance

Investigators receiving federal funding must adhere to the Code of Federal Regulations (CFR) to protect research participants and produce reliable study information. Sites participating in research sponsored by the NICHD need to have an internal quality assurance (QA) plan that will identify problems and correct errors in research study records.

7.6 Role of Data Management

The AC will provide instructions concerning the recording of study data on CRFs, and the entry and transmission of the data, and administration and transmission of CASI data.

7.7 Study Site Monitoring and Record Availability

Site monitors from the MC may visit participating study sites to review a selected portion of the individual participant records, including assent/consent forms, CRFs, and supporting source documentation to ensure the protection of study subjects, compliance with the protocol, and accuracy and completeness of records. Regulatory files, as required, will also be inspected to ensure that regulatory requirements are being followed.

The site investigator will make study documents (e.g., assent/consent forms, case report forms) *and pertinent hospital or clinic records* readily available for inspection by the local IRB, the central IRB, the site monitors, the NICHD, the Office for Human Research Protections (OHRP), or the sponsor's designee for confirmation of the study data.

8.0 PARTICIPANT MANAGEMENT

8.1 Tracking Participants / Follow-up

All subjects will be contacted before each follow-up study visit/assessment (i.e., enrollment, 3-month, and 6-month time points). Multiple contact methods will be used for youth who are difficult to reach (e.g., mail, alternate phone numbers, e-mail, text message, Facebook). Subjects will be asked whether or not messages can be left for each of the phone numbers that they provide. They will be informed that messages will not contain any information regarding the nature of the project. The SMART participant management system will be used.

8.2 Compensation

The method for compensation will be determined separately by each site and approved by each site's IRB. Participants at all sites will be compensated using the following cash or cash equivalent:

Usability test participants: Compensated with \$50.

Field test participants: Compensated with \$50 at first visit and \$50 at second visit. Possible to earn an additional \$45 for app usage over the 4-week field trial (\$145 total).

RCT participants: Compensated with \$50 at enrollment visit, \$50 at the 3-month visit, \$50 at the 6-month visit. Participants randomized to the P3 or P3+ arms have the possibility of earning an additional \$135 for app usage over the 3-month app intervention period (\$150 total control group/\$325 P3/P3+ group). Participants who complete an exit interview will earn an additional \$50. Participants who complete enrollment remotely will receive \$50 for specimen collection and \$50 for survey completion and intervention onboarding. Participants who began the study in-person and had to continue follow-ups remotely will receive \$50 for specimen collection and \$50 for survey completion.

Compensation will be provided in person or can be mailed to subjects, if allowed at the SRV.

8.3 Intervening on “Social Harms”

We identified the following 5 items as possible risks to subjects and described how we plan on addressing those risks:

- 1) Breach of Confidentiality: A potential risk to participants is violation of confidentiality. We will take the utmost caution to protect the confidentiality of all responses. We will minimize this risk by maintaining confidentiality and discretion throughout the usability testing, field testing and RCT. Files – audio, paper and electronic– will not have any identifying information about the study participants and will be tracked through a unique SID and participant code. All audio recordings will be downloaded and stored on a password-protected, encrypted computer in locked offices at UNC-CH and subsequently transferred to Emory’s secure Box or Microsoft OneDrive platform. Transcription of audio files will be conducted using a HIPAA compliant transcription service. Any names mentioned in the audio files will be redacted during transcription. Interview transcripts will be kept on Emory’s secure Box or Microsoft OneDrive platform. Analysis of transcripts will be conducted on a password-protected, encrypted computer. Hard copies will be kept in locked files. This research specifically targets a vulnerable population, children (YMSM ages 16-17). We will take every available step to minimize the risk of identifying/linking data being subpoenaed, stolen, or inadvertently released. First, the iTech has acquired a Certificate of Confidentiality from the NIH. Second, all research staff members are required to complete ethical clearance certification regarding protection of human’s subjects through the UNC-CH and/or Duke University. Third, the study will safeguard against the risk of the linking information being stolen by keeping such information in a locked Excel file store on a secure server at Emory University to which only essential study personnel who have completed CITI certification for human subjects’ research ethics training (<http://citiprogram.org>) will have access. We have also included numerous features to ensure app security and privacy. All relevant app communications (e.g. those between participants or those between participants and staff) will be secured via industry standard encrypted SSL communications links. These connections will ensure that all communications are inaccessible to unauthorized third parties. Furthermore, the app can be updated regularly to address any unforeseen security updates to the software libraries underlying the secured communication links. Beyond encrypting communication, we will allow users to enable an extra PIN to secure the app within their phone beyond the PIN required to unlock the phone itself. This will allow the user to share their phone generally with others without granting access to P3. These software security solutions will provide the layers of both communications security and physical access security to ensure that only authorized users have access to the information stored on the phone as well as the information being shared over communications links. We will take special care to ensure that P3 addresses participant privacy. We have chosen the app name, P3, because it does not relate to health care and is therefore designed to be non-stigmatizing and un-interpretable by anyone observing a participant using the app on their mobile phones. During app onboarding, study staff will assist youth in choosing a discreet and anonymous username. Moreover, mobile phone screens themselves are also constructed to prevent surreptitious observation.

- 2) Emotional discomfort: It is possible that the study may precipitate discomfort and/or an emotional response when YMSM/YTW who have sex with men answer questions about potentially sensitive topics such as HIV risk behaviors, STIs and medication adherence. Further, participants may feel embarrassed about discussing sensitive issues. All participants will be told during the informed consent process that their participation is voluntary and that they can choose to stop participating at any time without any consequences. Based on our experiences using similar data collection methods with YMSM/YTW who have sex with men in past studies, the likelihood and seriousness of this risk is minimal and we will strive to create a safe and comfortable environment for all study participants.
- 3) Discomfort during collection of whole blood and hair specimen: The risk of discomfort due to blood and hair sample collection is considered minimal. Physical harms are minimal. The type of safety lancet selected for use in the study was designed to minimize the potential for infection or significant injury. Cleaning the area with an alcohol pad first lowers the already low infection risk further; pads are included in every kit. The spring-loaded lancet retracts fully after one firing, and thus does not pose a risk for “needle stick” injury to anyone after the device has been used. Subjects could experience dizziness, diaphoresis and nausea associated with the procedure but in prior clinical studies using dried blood spots, adverse events have been rare. The risk of discomfort due to hair sample collection is considered minimal. Physical harms are minimal. There is some possibility of discomfort during the procedure related to lifting the hair away from the occipital region of the scalp. There is also the possibility of small nicks to scalp with scissors that may result from cutting the hair sample.
- 4) Protecting against hostile interactions and inaccurate information from one participant to another. Field trial participants and RCT participants assigned to the intervention study arms will be informed during the consent process of the “group rules” regarding interactions with one another (e.g., “Honesty is important; however, hostile or abusive language will not be tolerated and may be grounds for immediate removal from the study”). These “terms of use” will also be available with a link on the app for review by participants at any time. The UNC based project coordinator and/or research assistant will manually review participants posts on a daily basis to identify any hostile interactions or inaccurate information. Hostile interactions between participants will be handled by, first, reminding the participants in the interaction of the “group rules” regarding appropriate interactions. If the hostility continues, the offending participants will be given a warning that the continued hostility will result in withdrawal from the study if it continues. On the third offense, the offending participant will be withdrawn from the study. Text containing hostile exchanges will be removed from the study app and unavailable to view. In cases in which inaccurate information is found, project staff will be guided by experts on the team to post a comment that provides accurate information on the topic. In extreme cases, the PI’s may decide to withdraw a participant before the third offense. We will ensure all SRVs have a clear clinical protocol to address major issues that may come up at study visits or in online interactions. The major issues addressed in the protocol will be suicidal ideation, homicidality or violent ideation, emotional and cognitive disregulation, violent/aggressive or disruptive behavior, and intoxication. If research staff from the University of North Carolina see concerning comments or messages online from participants regarding self-harm or harm of others, they will contact clinicians at the site and take immediate precautions.

All sites have specific policies governing the treatment of human subjects. These policies specify that medical and psychological assistance will be available in the immediate environment in the event a participant should experience any adverse reactions resulting from study procedures.

While participants will be informed that they may refuse to answer any question at any time, responses or reactions to certain questions may indicate distress on the part of the participants. If at any time during the study, a participant divulges that they are at risk for harm, including but not limited to being abused or experiencing violence, if harm is suspected or likely, or if the participant states

they are suicidal/homicidal, measures will be taken to ensure their safety. Reporting will be done as appropriate to the situation and the legal statutes, including reporting to child protection agencies or other appropriate agencies, and referrals will be provided to appropriate support, counseling, or treatment resources.

8.4 Criteria for Premature Study Discontinuation

The principal investigator has the authority to withdraw any participant at any time if it their opinion it would be in the best interest of the participant. The participant will be informed of this withdrawal and explained the rationale. Withdrawal will be documented in the study tracking system.

Subjects will be prematurely discontinued from the study if any of the following occurs:

- The subject withdraws consent/assent;
- The subject reports testing HIV-positive at follow-up assessments;
- The study is cancelled by the *NIH (or iTech, or other administrative entity)*;
- The study is cancelled for other administrative reasons;
- The participant repeatedly posts hostile or inflammatory information on the app (see Section 8.3)
- The subject becomes incarcerated or placed in detention during the study; or
- Death of the subject.

Participants may end their participation in the study at any time. No further data collection will occur from the date the decision is made to permanently discontinue the subject from the study. Participants who experience distress during the study while in the SRV clinic will be offered counseling on site. Participants who experience distress during the study and do not come to the SRV clinic for a visit will be provided a list of community referrals via phone or e-mail. Any unexpected adverse events that meet the new safety information reporting criteria will be immediately reported to the UNC-CH IRB and the respective sites' IRBs if applicable. The *Study Stop and Adverse Event Forms* will be completed at this time.

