The checklist for the Enrollment Visit can be found in the Baseline RCT Checklist. During the in-person enrollment visit, youth who are eligible for the study will be guided through an informed consent/assent process by research staff. After participants are consented, whole blood specimen will be collected and it will be documented on the Specimen Collection CRF. Next, they will complete a computer-assisted baseline survey (CASI), created by AC staff and hosted on Alchemer, a secure, HIPAA-compliant platform. Study staff will document whether consent was obtained and the participant's enrollment status on the Screening and Enrollment CRF.

Next, participants who are enrolled will be randomized 1:1:1 ratio into the P3 and P3+, or standard of care arm based on a randomization sequence developed by the AC and loaded into DFExplore clinical data management software. The randomization sequence will be stratified by SRV. Participants randomized to the P3 or P3 + arms will be guided through the app download process by SRV staff and given an app site tour to highlight features. Those in P3+ arm will be provided with additional information about the Next Step Counseling component (adherence counseling) including information about how to contact the counselor through the app. Participants will be considered enrolled upon meeting all RCT eligibility criteria, signing the enrollment RCT consent/assent form, being randomized to P3, P3 + or control and for P3, P3 + group, completing the baseline CASI, successfully downloading the app on their phones. Once participants have completed these tasks (see Baseline Checklist), they will be compensated \$50 for their time.

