P3 and P3+ arms: After giving a brief description of the relevant intervention study arm, SRV site staff will help the participant download and install P3 on the subject's phone and provide a guided tour of the app. If the visit is done remotely, the participant will be sent a link to a video to guide them through downloading, installing, and reviewing the app. They will be sent their App ID through text in SMART. The adherence counselor texting portal will be unlocked and demonstrated for those in the P3+ arm. The participant will then be instructed to send an introductory text to the adherence counselor through the portal and encouraged to schedule their first adherence counseling session. SRV site staff will provide assistance if needed. Each individual will be given SRV staff phone number and email address and instructed to contact them immediately to report difficulties with any app components or to report any problems with their phone or phone service. P3 arm participants will have access to all features of P3 except the adherence-counseling component. P3+ participants will have access to all features of P3. The duration of the intervention is 3 months for both intervention arms. However, participants will still have access to the P3 app after the completion of 3 months until the end of the trial. They will not have access to the adherence counselor feature (in either the P3 or P3+arm) and the virtual bank account feature will not be active (e.g. they will not receive additional monetary incentives for using the app)

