6.2.1 Administrative and Behavioral Procedures

Confirmation of active prescription by pill bottle, photograph of pill bottle, or chart review of filled prescription and verification of ID through either the medical record or with photo ID (driver's license, state ID, school ID card) to confirm the PrEP prescription belongs to the individual.

Informed Consent/Accent

Baseline Assessment using CASI

Randomization to P3, P3+ or control

For P3 and P3+ intervention participants, download and set-up of P3 app

For P3 and P3+ intervention participants, tour and training on the P3 app

For P3+ intervention participants, training and initiation on the NSC feature

For control participants, provision of control materials/resources

Completion of participant contact/tracking information

Remuneration for survey completion

For remote participants, mailing of self-collection specimen kit and specimen collection
CASI

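### Withdrawing participants from the whole study for hostile app posts creates avoidable outcome loss that only the P3/P3+ arms can incur, of unknown size and direction

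*Protocol*

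**What the plan says.** Protocol 8.3 sets out an escalation for hostile posts: a reminder, a warning, and then "On the third offense, the offending participant will be withdrawn from the study". Discretion allows this sooner: "In extreme cases, the PI’s may decide to withdraw a participant before the third offense". Section 8.4 repeats the criterion ("The participant repeatedly posts hostile or inflammatory information on the app") in its list of reasons for discontinuation from the study. It gives the consequence for data: "No further data collection will occur from the date the decision is made to permanently discontinue the subject from the study". Neither section provides for ending app access while outcome collection continues.

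The app goes to two of the three arms. Protocol 5.1 says "Participants randomized to the P3 or P3 + arms will be guided through the app download process by SRV staff"; for the third arm, 6.2.1 lists "For control participants, provision of control materials/resources". Within the RCT, 8.3 addresses the posting rules to the intervention arms. Exposure to the rule lasts for all of follow-up, because under 5.4.3 "participants will still have access to the P3 app after the completion of 3 months until the end of the trial".

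Protocol 10.3.4 refers to the preceding efficacy analyses as ITT. SAP 4.2 models the probability of an observed outcome from treatment indicators, age, baseline DBS, baseline PrEP use, site and race/ethnicity. SAP A.2 assumes that no post-baseline variable affects both missingness and the outcome.

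**The concern.** The rule joins two events that an ITT comparison needs to keep apart: stopping the intervention and stopping measurement. A P3 or P3+ participant removed for posting conduct may not have withdrawn consent to be measured, yet the plan ends the blood samples and surveys anyway. No SOC participant can be lost this way. The other listed criteria (withdrawn consent, a reported HIV-positive test, incarceration, death, study cancellation) can apply in any arm.

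At stake is the primary contrast, P3/P3+ versus SOC in the proportion with protective drug levels. If those removed differ in adherence from otherwise similar people who stay in the same arm, the P3/P3+ proportion is biased and SOC has no matching loss. The loss is small in any plausible scenario, but the protocol itself creates it and could avoid it.

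**Working it through.** **1. Who can be removed.** Allocation is 80 per arm (Protocol, Study Abstract and 3.2). Exposed to the rule: 80 + 80 = 160. Not exposed: 80.

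**2. The plan's own loss figure.** Protocol 10.2.3 expects 20% loss by month 3: 240 × 0.80 = 192, or 64 per arm, which reproduces. In P3/P3+ this is 0.20 × 160 = 32 people. The documents do not say whether posting removals are counted within the 20%.

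**3. What is lost, by timing.** Removal before month 3 loses both follow-up assessments. Removal after the month-3 assessment loses month 6 only, since 8.4 stops further collection and does not discard earlier data.

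**4. Whether the analysis can recover it.**
- The missingness model contains treatment indicators, and SAP Table 15 adds treatment interactions with age and baseline DBS for some learners. Different loss rates by arm are therefore modelled. What is not modelled is selection within an arm on post-baseline conduct.
- SAP 6.2 and A.5 use same-visit self-report to inform missing DBS results. After withdrawal there is no survey either.
- Under SAP A.5.4, a person with neither DBS nor survey receives a prediction from the regression for observed DBS outcomes, given baseline covariates and arm. This is unbiased only if conduct carries no further information about adherence.

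**5. Size of the bias.** Let *p* be true adherence in P3/P3+, *k* the fraction removed before month 3, and *q* adherence among those removed. With outcomes taken only from those who remain,

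shift = (p − kq)/(1 − k) − p = k(p − q)/(1 − k).

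This leaves out any correction from baseline covariates. Take *p* = 0.27 + 0.14 = 0.41, using the SOC rate and the 14-point effect in Protocol 10.2.3. The range *k* = 1-5% is an assumption (1.6 to 8 of 160).

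| Adherence of those removed | k = 1% | k = 5% |
|---|---|---|
| None protected (q = 0) | 0.01 × 0.41/0.99 = +0.4 points | 0.05 × 0.41/0.95 = +2.2 points |
| Half the arm's rate (q = 0.205) | 0.01 × 0.205/0.99 = +0.2 | 0.05 × 0.205/0.95 = +1.1 |
| Same as the arm (q = 0.41) | 0 | 0 |
| All protected (q = 1) | 0.01 × (−0.59)/0.99 = −0.6 | 0.05 × (−0.59)/0.95 = −3.1 |

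**6. Effect on the test.** Assume no true effect (27% in both groups), all removed participants non-adherent, and 20% other loss. With *m* removed, the apparent P3/P3+ proportion is 0.27 × 160/(160 − m), on 128 × (160 − m)/160 participants, against 64 in SOC. For *m* = 8 this is 43.2/152 = 0.284 on 121.6. The standard error is √(0.27 × 0.73/64 + 0.284 × 0.716/121.6) = 0.069, so the shift is 0.014/0.069 = 0.21 standard errors. Two-sided rejection at nominal 0.05 is then 0.055. For *m* = 2, 4 and 16 it is 0.050, 0.051 and 0.071.

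**The case against.** The strongest case against acting is that the effect is negligible and its direction is a guess. Much of this stands. A reader might infer that the rule inflates the intervention effect, on the view that hostile posters adhere poorly. The documents do not support that: nothing in them links hostile posting to adherence. Reaching a third offence takes continued use of the app, so those removed could be engaged users with average or better adherence. The range in the table crosses zero.

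The size argument also stands. Two to eight removals are few beside the 32 losses planned for in P3/P3+, and SAP 6.2 already expects high DBS missingness because of COVID-19. Daily review of posts and the reminder and warning steps make third offences less likely.

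Two further inferences go too far. One is that everyone removed loses both follow-up assessments; later removals keep month 3. The other is that the missingness model ignores arm; it does not.

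It can also be said that reporting is partly covered: 8.4 calls for a Study Stop form, and SAP Table 14 shows missing outcomes by arm. Neither the table nor the text, however, separates posting removals from other loss.

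Finally, SAP 6.1 gives 24 February 2022 for data availability, so an amendment may be too late to recover samples already missed. That limits what can be done for this dataset; it does not make the rule sound. None of these points explains why outcome measurement has to stop when app participation does.

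**Conclusion.** The point holds as a design weakness of modest consequence. Sections 8.3 and 8.4 impose avoidable, arm-specific, post-randomisation outcome loss on a comparison called ITT, and the planned analysis cannot correct for any part of it that depends on conduct after baseline. Size and direction are unknown. Under the assumed 1-5% removal before month 3 and 41% true adherence, the month-3 P3/P3+ proportion could be anywhere from 3.1 points too low to 2.2 points too high. These limits need the extreme assumption that all, or none, of those removed were protected. If they adhere like the rest of their arm, there is no bias. The error rate of the test barely moves for 2 to 8 removals. The documents do not support a claim that the trial's result is biased in favour of the app.

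**What to change.** Reconcile Protocol 8.3 and 8.4 with the ITT analysis by stating that removal for posting conduct does not by itself end outcome collection. Where the participant continues to consent, collect the month-3 and month-6 blood sample and survey and analyse them in the randomised arm. Sections 6.3 and 6.4 already provide mailed self-collection kits and emailed survey links, so this need not involve contact with other participants. The moderation and conduct rules are for the investigators; the change concerns outcome collection only.

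Add to the SAP a count of posting-rule removals by arm and by time point (before month 3, or between months 3 and 6). If follow-up is complete, this count is the part that can still be done. It lets a reader bound the bias with the formula above.

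The cost is a small amendment to the protocol and to the consent wording, because the posting rules are explained at consent, together with IRB review and a few extra remote contacts.
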